6.19 Study Eye Selection Process

Subjects must qualify in both eyes based upon IOP, ocular history and exam; the study eye will be the eye with the higher IOP at 09:00 hours on Visit 3. If both eyes have the same IOP at 09:00 hours on Visit 3, then the right eye will be the study eye. For each subject, BOTH eyes will be treated.

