7.1.2 Washout

As noted in Section 5.7.1, a washout period is required for individuals currently using ocular hypotensive medications and who meet the other qualifications for enrollment.

7.2 Visit 2 (Qualification Visit #1, for IOP and safety measurements at 09:00 hours)

After the washout (if needed), individuals will return to the Investigator's office in the early morning. The subject will be questioned regarding any changes in their health or concomitant medication use. Any change in the individual's Visit 1 health status should be recorded on the Medical History page of the CRF (e.g., the subject has been diagnosed with cancer).

Inclusion/exclusion criteria will be reviewed again for the qualified individual. Results of the clinical laboratory tests from Visit 1 need to be available and reviewed by the Investigator.

For subjects who were unable or unwilling to have blood drawn and urine collected for the clinical labs at Visit 1, the blood and urine sample may be drawn at Visit 2 (Qualification Visit #1) so long as the results of the clinical labs are available for that subject prior to Visit 3 (Qualification Visit #2).

The following procedures will be performed:

- Heart rate and blood pressure

- Symptomatology: Individuals will be asked “How are you feeling?”
- BCVA
- A non-dilated eye examination will be performed, including IOP measurements and biomicroscopy. IOP must be measured between 09:00 and 09:30 hours.

For further evaluation of OAG eyes in the study, at this time, unmedicated (post washout) IOP must be ≥ 15 mmHg and < 35 mmHg in both eyes. For further evaluation of OHT eyes in the study, at this time, unmedicated (post washout) IOP must be ≥ 22 mmHg and < 35 mmHg in both eyes. **This is the first of the four qualifying IOPs for randomization.**

Individuals who do NOT meet the IOP requirements above may return for up to 2 additional qualification visits within 1 week of failing this qualification visit. Individuals returning for an unscheduled visit within 1 week to re-attempt IOP qualification are required to only re-measure IOP in both eyes.

Individuals who screen fail due to IOP being ≥ 35 mmHg in either eye (exclusion criterion) MAY NOT return for additional qualification visits.

Qualified individuals will be scheduled to return 2-7 days later for the second qualification visit.

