Mean percent change from baseline in mean diurnal IOP and mean percent change from diurnally adjusted baseline IOP at each time point will be analyzed using two-sample t-tests, between netarsudil (0.01%, 0.02% or 0.04%) and placebo, at each time point and visit, including two-sample t-tests and 95% t-distribution confidence intervals on the difference (netarsudil - placebo).

Mean diurnal IOP values will be constructed by averaging the 3 diurnal IOP measurements on each of Week 1, Week 2, and Week 4 visits. Mean diurnal baseline IOP will be constructed as the average of the three Day 1 IOP measurements. Mean change from mean baseline diurnal IOP will be created by taking the average of the 3 time points on each of Week 1, Week 2, and Week 4 visits and subtracting the single mean baseline diurnal IOP measurement.

Sub-group analyses based upon pre-study characteristics such as site, demographics, baseline IOP categories, or pre-study ocular hypotensive medications may be completed to further investigate the efficacy measures.

Analyses of IOP will also include summarizing the number and percentage of study eyes achieving mean diurnal IOP reduction from baseline of ≥ 4 to ≥ 12 mmHg in 2 mmHg increments and percent reduction from baseline of $\geq 5\%$ to $\geq 40\%$ in 5% increments at Week 1, Week 2, and Week 4. Additionally, the number and percentage of study eyes attaining a mean diurnal IOP of ≤ 22 to ≤ 14 mmHg in 1 mmHg increments will be summarized at Week 1, Week 2, and Week 4. Fisher's exact test (2-sided p-values) will be used to test differences between netarsudil (0.01, 0.02% or 0.04%) versus placebo for each category at each visit. These analyses will be presented for both the ITT and PP populations with observed data only.

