4.2 Masking

Treatment assignments will be masked to the Investigator, the clinical study team (Sponsor, personnel involved in day to day study management, Monitors, Data Managers, and Statisticians), and the subjects for the duration of the study. Only in case of medical emergency or occurrence of AEs that warrant unmasking in the opinion of the Investigator, will the treatment assignment(s) be unmasked and made available to the Investigator and the Sponsor Medical Monitor or designee. Individual unmasking by the Investigator will normally result in withdrawal of the subject from the study and should only be performed for the specific subject requiring unmasking. In the absence of medical need, the randomization code will not be available to the above personnel until after the study is completed and the database is unlocked.

5. Sample Size and Power Considerations

Assuming a two-sided test with alpha = 0.05, a common standard deviation (SD) of 3.5 mmHg at each time point yielding a common SD of 3.0 for the diurnal mean, and a correlation among time points of 0.60, 49 intent-to-treat (ITT) subjects per arm yields at least 90% power to demonstrate superiority of netarsudil (0.01%, 0.02%, or 0.04%) to placebo in mean diurnal study eye IOP (average of 09:00, 11:00, and 16:00 hours) at the Week 4 visit assuming a difference of at least 2.0 mmHg in the mean diurnal IOP. Accounting for approximately a 5% discontinuation rate, 52 subjects per arm (208 total) will be enrolled.

6. Data Preparation

Study data will be recorded via electronic case report forms (eCRF). Each authorized study staff member will receive a unique access account in order to use the Electronic Data Capture (EDC) system. Access accounts will not be shared among study staff. Authorized users will make entries and/or changes to the eCRFs via a secure internet access. Each completed set of eCRFs will be reviewed by the Investigator

who will then electronically sign and date the eCRF confirming that data for the subjects are complete and accurate.

Final analyses outlined in this document will be carried out after the following have occurred:

- All data management requirements are met according to [REDACTED] standard operating procedures, including data entry, performance of edit and validation checks, documentation and resolution of data queries, and database lock with written authorization provided by appropriate [REDACTED] and Sponsor personnel.

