13.1 Primary Efficacy Analysis

The primary efficacy endpoint will be the mean of mean diurnal IOP at Week 4 (Day 29). The primary analysis of the primary endpoint will employ an analysis of covariance (ANCOVA) model with mean of mean diurnal IOP at Week 4 as the response, baseline mean of mean diurnal IOP as a covariate, and treatment as a main effect, using the ITT population with MCMC multiple imputation techniques used to impute missing data. The least squares (LS) mean differences (netarsudil – placebo) will be presented separately for netarsudil 0.01%, 0.02%, and 0.04% as well as two-sided p-values and 95% CIs. For a given comparison, if the p-value is <0.05 and the point estimate of the LS mean difference is < 0, then the netarsudil group will be considered superior to the placebo.

The following SAS code will be used for multiple imputations using the MCMC method:

```
proc mi data = inidata seed = 48669 out = outdata1;
  mcmc initial = em;
  var trt01pn baseline IOP;
  run;
  where
    - inidata is the name of the input dataset
    - outdata is the name of the output dataset
    - trt01pn is the name of the treatment group variable in numeric format
    - baseline is the corresponding baseline IOP for a given time point
    - IOP is the name of the IOP measure.
```

Five (5) complete data sets will be generated from the above code. Each complete data set will be used to analyze this primary efficacy endpoint separately using ANCOVA. Then, the SAS procedure MIANALYZE will be used to analyze the results from the 5 complete data sets to generate a combined inference. The following SAS code will be used:

```
ods output diffs = outdata2;
proc mixed data = outdata1;
  class trt01pn;
  model IOP = trt01pn baseline;
  lsmeans trt01pn / cl pdiff;
```

```

by _Imputation_;
run;

proc sort data = outdata2;
  by trt01pn trt01pn;
run;

ods output ParameterEstimates = outdata3;

proc mianalyze data = outdata2 alpha = 0.05;
  by trt01pn trt01pn;
  modeleffects estimate;
  stderr stderr;
run;

```

where

- *IOP* is the name of the IOP measure
- *trt01pn* is the name of the treatment group variable in numeric format
- *outdata2* is the name of the output dataset that contains the statistical results of the differences between treatment groups
- *outdata3* is the name of the output dataset that contains summary and inferential statistics.

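### The primary ANCOVA leaves out the Visit 2 unmedicated IOP; adding it is a free improvement that narrows the baseline-adjusted intervals modestly, and the planned analysis is valid without it

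*SAP*

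**What the plan says.** - **Model.** SAP 13.1 specifies an ANCOVA for Week 4 mean diurnal IOP with "baseline mean of mean diurnal IOP as a covariate, and treatment as a main effect, using the ITT population". Missing values are filled by MCMC multiple imputation from treatment, baseline IOP and IOP.
- **Baseline.** Protocol 9.6.2: "Mean diurnal baseline IOP will be constructed as the average of the three Day 1 IOP measurements". All three readings (09:00, 11:00, 16:00) come from Visit 3.
- **Study eye.** Protocol 6.19: "the study eye will be the eye with the higher IOP at 09:00 hours on Visit 3". The covariate therefore includes the reading that selects the eye.
- **Visit 2.** Protocol 7.2 measures post-washout IOP in both eyes at 09:00, with Visit 3 following 2-7 days later. It states: "This is the first of the four qualifying IOPs for randomization". The value therefore exists before randomization for every properly randomized subject. It enters none of the efficacy models in SAP 13.1-13.3 or Table 13-1.
- **Precision assumptions.** SAP Section 5 takes 3.5 mmHg as the SD of a single reading and describes this as "yielding a common SD of 3.0 for the diurnal mean, and a correlation among time points of 0.60". It takes no credit for covariate adjustment and gives no correlation between visits.

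**The concern.** Readings taken on one day share whatever deviation that day brings, and averaging three of them does not remove it. A reading from another untreated day carries separate information about the eye's usual pressure, so it should explain some of the Week 4 variance that the Day 1 mean leaves behind. What is at stake is the width of the adjusted netarsudil-placebo intervals. The study title also names finding the best concentration as an aim, and tighter estimates help there. The gain would need no extra subject, visit or measurement.

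**Working it through.** **1. The plan's own figure.** Inputs from SAP Section 5: SD 3.5 mmHg per time point, within-day correlation 0.60, difference 2.0 mmHg, two-sided alpha 0.05, 5% discontinuation.

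- SD of the diurnal mean = 3.5 × √[(1 + 2 × 0.60)/3] = 2.997, stated as 3.0.
- Noncentral-t power at SD 3.0 is 0.898 with 48 per arm and 0.904 with 49, so 49 is confirmed.
- 49/0.95 = 51.6, rounded up to 52; 4 × 52 = 208.

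**2. Residual variance with and without Visit 2.** Let *r* be the correlation of a Week 4 reading with a Day 1 or Visit 2 reading, and *d* the correlation of the Visit 2 reading with a Day 1 reading. The documents give neither, so both are assumptions.

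- Variance of a single reading: 3.5² = 12.25.
- Variance of a daily mean: V = 12.25 × 2.2/3 = 8.983.
- Covariances: C = 12.25*r* and D = 12.25*d*.
- Day 1 mean only: V − C²/V.
- Day 1 mean plus Visit 2: V − C²(V + 12.25 − 2D)/(12.25V − D²).
- Excess width of the planned interval: square root of the ratio of the two, minus 1.

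Example, *r* = *d* = 0.5 (C = D = 6.125):

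- Day 1 only: 8.983 − 37.516/8.983 = 4.81.
- With Visit 2: 8.983 − 37.516 × 8.983/72.530 = 4.34.
- Excess: √(4.81/4.34) − 1 = 5.3%.

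| *r* (with Week 4) | *d* (Visit 2 with Day 1) | Day 1 only | Plus Visit 2 | Planned interval wider by |
|---|---|---|---|---|
| 0.4 | 0.4 | 6.31 | 5.79 | 4.4% |
| 0.5 | 0.5 | 4.81 | 4.34 | 5.3% |
| 0.6 | 0.6 | 2.97 | 2.68 | 5.2% |
| 0.4 | 0.5 | 6.31 | 6.01 | 2.5% |
| 0.5 | 0.6 | 4.81 | 4.61 | 2.1% |
| 0.4 | 0.6 | 6.31 | 6.18 | 1.0% |

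The lost degree of freedom takes about 0.3 percentage points off the common-correlation rows (5.2% becomes 4.9%). Over a common correlation of 0.2 to 0.65 the excess runs from 1.7% to a maximum of 5.4%. Over a wider set of unequal pairs (*r* from 0.3 to 0.6, *d* above *r* and up to 0.7) it runs from about 0.1% to 3.6%.

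**3. Absolute size.** At *r* = *d* = 0.5 and 52 per arm, the SE of a difference falls from √(2 × 4.81/52) = 0.430 to √(2 × 4.34/52) = 0.408 mmHg. That is about 1.96 × 0.022 = 0.04 mmHg of half-width. In sample-size terms it is worth 52 × (4.81/4.34 − 1), or 5 to 6 subjects per arm.

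**4. Eye selection and entry limits.** In simulations with an assumed between-visit correlation of 0.4-0.6 and assumed mean IOPs of 18-24 mmHg, higher-eye selection alone left the excess at 4.4-5.3%. Adding the entry limits gave 2.8-4.8%. A separate simulation of mixed populations (assumed 30-40% OHT) gave 4.8-5.9%. All of these rest on assumed IOP distributions.

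**The case against.** The strongest reply is that nothing here is wrong. A baseline-adjusted ANCOVA is valid in a randomized comparison. Sample size was set on the unadjusted SD, so the planned covariate already brings spare power: at 49 per arm with the Day 1 covariate alone, it is 97.6% at a between-visit correlation of 0.4 and above 99% at 0.5. The documents set no target for interval width. All of this stands, and it is why the point is only an improvement.

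The size also depends on a correlation that the plan does not state. Visit 2 and Day 1 are days apart and both untreated, whereas Week 4 is about four weeks later and on treatment in three arms. It is plausible that Visit 2 tracks Day 1 more closely, which gives the lower rows of the table. The 0.6 case also equals the same-day correlation, so it contains no day-specific deviation; Visit 2 then acts simply as a fourth reading. This stands too.

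Four stronger readings that a reader might infer are not supported:

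- **That choosing the eye by a Day 1 reading biases the comparison.** The choice is made before randomization (Protocol 7.3.3), so it cannot favour an arm.
- **That every interval is affected.** The two-sample t-test intervals in SAP 13.2 use no covariate. The figures above were not derived for the MMRM or the single-time-point ANCOVAs.
- **That the loss reaches about 8%.** Visit 2 alone does not get there at the documented 0.60; that would need a within-day correlation of about 0.8 or more. Values near 8% appeared only when study-eye diagnosis was added as well, under assumed IOP distributions.
- **That Visit 2 plays no part in choosing the eye.** SAP 8.1 allows for a subject qualifying in one eye only, and Visit 2 IOP is part of qualifying, although Protocol 6.19 requires both eyes to qualify. Visit 2 remains a legitimate pre-randomization covariate either way.

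**Conclusion.** The point holds as a free improvement. A pre-randomization predictor that the trial already collects is left out of the primary model, and including it would narrow the baseline-adjusted ANCOVA intervals. The planned intervals are about 4-5% wider than with Visit 2 added if one between-visit correlation of 0.4-0.6 applies throughout. They are about 1-2.5% wider in the cases shown where Visit 2 correlates more with Day 1 than with Week 4. Both ranges assume the plan's SD of 3.5 and within-day correlation of 0.60, and between-visit correlations that the documents do not give. No conclusion about validity, bias or inadequate power follows.

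**What to change.** In SAP 13.1, add the study eye's qualifying Visit 2 09:00 IOP as a second baseline covariate. Put the same variable in the PROC MI variable list and the PROC MIXED model statement, so that the imputation and analysis models match.

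State which reading counts. Protocol 7.2 lets a subject who misses the IOP limits return for up to two further qualification visits, while SAP 8.5 drops unscheduled visits unless they serve as baseline. The SAP should say that for requalified subjects the qualifying reading is used, as an explicit exception to 8.5.

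Make the change before treatment codes are unmasked. SAP 13.3 and Section 20 describe some analyses in the past tense, so this needs checking. If codes are already unmasked, keep the planned model as primary and report the extended one only as a labelled supportive analysis.

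The cost is one covariate term and its code, the requalification rule, and one residual degree of freedom (with 208 subjects, 203 under the planned model). No new data are needed.

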Appendix 6 Sample SAS Code

The following SAS code will be used for multiple imputations using the Monte-Carlo Markov Chain method, where a separate model will be fit for each time point at each visit.

```
proc mi data = indata seed = 6876 out = outdata1;  
  
mcmc initial = em;  
  
var trt01pn baseline IOP;  
  
run;
```

where

- *indata* is the name of the input dataset
- *outdata1* is the name of the output dataset
- *trt01pn* is the name of the treatment group variable in numeric format
- *baseline* captures the baseline IOP for the given time point
- *IOP* is the name of the IOP measure.

Thirty complete data sets will be generated from the above code. Each complete data set will be used to analyze this primary efficacy endpoint separately using analysis of variance. Then, the SAS procedure MIANALYZE will be used to analyze the results from the 30 complete data sets to generate a combined inference. The following SAS code will be used:

```
ods output diffs = outdata2;  
  
proc mixed data= outdata1;  
  
by _IMPUTATION_;  
  
class trt01pn;  
  
model IOP = trt01pn baseline;  
  
lsmeans trt01pn / cl pdiff;  
  
run;  
  
proc sort data= outdata2;  
  
by trt01pn _trt01pn;
```

```
run;  
  
ods output ParameterEstimates = outdata3;  
  
proc mianalyze data= outdata2 alpha = 0.05;  
    by trt01pn _trt01pn;  
    class trt01pn _trt01pn;  
    modeleffects estimate;  
    stderr;
```

run;

where

- *outdata1* is the name of the input dataset from Proc MI
- *_IMPUTATION_* is the imputation number
- *trt01pn* is the name of the treatment group variable in numeric format
- *IOP* is the name of the IOP measure
- *baseline* captures the baseline IOP for the given time point
- *outdata2* is the name of the output dataset that contains the statistical results of the difference between treatment groups
- *outdata3* is the name of the output dataset that contains summary and inferential statistics.

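### The primary-analysis imputation treats the four arms as one linear numeric code and ignores Week 1 and Week 2 IOP, so the contrasts with placebo shift by an amount that depends on an unstated arm numbering

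*SAP*

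**What the plan says.** The primary analysis (SAP 13.1) is an ANCOVA of Week 4 mean diurnal IOP on treatment and baseline, in the ITT population, after MCMC multiple imputation. The SAS code is given as the code to be used.

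- The PROC MI step lists "var trt01pn baseline IOP". The treatment variable "is the name of the treatment group variable in numeric format". PROC MI has no CLASS statement, no BY statement and no arm indicators.
- The PROC MIXED step that follows declares "class trt01pn", so there treatment is a four-level factor.
- Protocol Appendix 6 has the same variable list, "where a separate model will be fit for each time point at each visit". Neither document puts Week 1 or Week 2 IOP into the Week 4 imputation, and neither says which number each arm receives.
- On the number of imputations, the SAP says "Five (5) complete data sets will be generated from the above code" and Protocol Appendix 6 says "Thirty complete data sets will be generated from the above code". Neither code block sets it.

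The sizing case (SAP Section 5) has 49 per arm for at least 90% power, "assuming a difference of at least 2.0 mmHg in the mean diurnal IOP", and then: "Accounting for approximately a 5% discontinuation rate, 52 subjects per arm (208 total) will be enrolled". The protocol synopsis applies that difference to each concentration.

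**The concern.** Under the MCMC normal model, a numeric arm code enters as one continuous variable. Missing values are then drawn from a model in which the four arm means lie on a line, but they are analysed by a model with four free means. The two agree only if the true means are linear in the code, which includes the case of no effect in any arm. The sizing case is not linear under any numbering: three equal active means at three different codes force a slope of zero, and then placebo would have to share that mean.

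The second gap is the earlier IOP. SAP 8.5 assigns early-termination efficacy data to the nearest visit by window, so a subject who stops around Week 2 has Week 1 and Week 2 IOP on file but no Week 4 value. The imputation ignores those readings. Two documented routes lead there:

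- Protocol 6.20.2 allows discontinuation for lack of efficacy shown by IOP, which ties dropout to data the model omits.
- SAP 3.1 requires stopping for cornea verticillata, which Protocol 1.1 calls dose dependent, so missingness may differ by arm.

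No rate by Week 4 is given for either. Superiority of each concentration is read from this analysis.

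**Working it through.** **1. The plan's own figure.** SD of the diurnal mean: 3.5 × √((1 + 2 × 0.6)/3) = 2.997, stated as 3.0. A two-sample t-test (difference 2.0, SD 3.0, two-sided 0.05) has 89.8% power at 48 per arm and 90.4% at 49. Then 49/0.95 = 51.6, so 52. The plan's 49 and 52 are reproduced.

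**2. Closed form for the arm coding.** Inputs: means relative to placebo of 0, −2, −2, −2 (sizing case); 5% missing at random in each arm; equal arms; codes 1 to 4, equally spaced (an assumption, since the documents give no codes).

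Slope = Σ(code − 2.5) × mean / 5. With placebo first: (0 + 1 − 1 − 3)/5 = −0.6, with overall mean −1.5.

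- Fitted means: −0.6, −1.2, −1.8, −2.4.
- Fitted minus true: −0.6, +0.8, +0.2, −0.4.
- Contrast shift = 0.05 × (error in active arm − error in placebo):
  - 0.01%: 0.05 × (0.8 + 0.6) = +0.07
  - 0.02%: 0.05 × (0.2 + 0.6) = +0.04
  - 0.04%: 0.05 × (−0.4 + 0.6) = +0.01

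Positive means toward no effect.

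| Placebo numbered | 0.01% | 0.02% | 0.04% |
|---|---|---|---|
| first | +0.07 | +0.04 | +0.01 |
| second | +0.11 | +0.09 | +0.08 |
| third | +0.08 | +0.09 | +0.11 |
| last | +0.01 | +0.04 | +0.07 |

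The shift scales with the missing fraction. At 10% missing, the placebo-first row becomes +0.14, +0.08, +0.02.

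**3. Simulation of the same case.** 4,000 trials, 52 per arm, 5 proper normal-model imputations, ANCOVA, assumed baseline correlation 0.6, Monte Carlo SE 0.002.

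- Placebo first: +0.070, +0.038, +0.006.
- Placebo last: +0.012, +0.041, +0.073.
- Treatment categorical in the imputation: +0.0005, +0.0008, −0.0019, so no detectable bias.

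**4. Other effects and missing rates (closed form).**

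- All 24 numberings, any effects between 0 and −2, 5% missing in every arm: −0.06 to +0.12.
- Effects −1/−2/−3: exactly zero with placebo first; +0.02/+0.08/+0.14 with placebo last.
- Effects −2/−3/−4: +0.035/+0.02/+0.005 with placebo first; +0.03/+0.10/+0.18 with placebo last.
- Missing 2/4/6/8% (placebo/0.01/0.02/0.04%), flat −2: +0.04/+0.02/−0.02 with placebo first; 0.00/+0.02/+0.08 with placebo last. The 0.04% contrast changes sign with the numbering alone.

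**5. Dropout that follows Week 2 IOP (illustrations, not bounds).** 2,000 simulated trials, 52 per arm, three clock times with SD 3.5 and correlation 0.6. Assumed: visit correlations of 0.6 (baseline to post) and 0.75 (post to post), and logistic dropout in Week 2 diurnal IOP with slope 1 or 2 per SD, 5% overall. Monte Carlo SE at most 0.005.

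| Effects, numbering | Slope | Missing % (placebo/0.01/0.02/0.04%) | Shift (0.01/0.02/0.04%) |
|---|---|---|---|
| flat −2, placebo first | 1 | 7.5/4.2/4.2/4.2 | 0.12/0.09/0.07 |
| flat −2, placebo first | 2 | 9.3/3.6/3.6/3.6 | 0.18/0.16/0.14 |
| −1/−2/−3, placebo last | 1 | 7.4/5.5/4.1/3.0 | 0.07/0.14/0.19 |
| −1/−2/−3, placebo last | 2 | 8.9/5.6/3.4/2.0 | 0.12/0.22/0.26 |

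With arm indicators but still without Weeks 1 and 2, 0.02 to 0.12 of bias remains. With indicators and Weeks 1 and 2 it is within 0.003. Imputing each clock time separately and then averaging gives the same bias as imputing the diurnal mean, within 0.003.

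**6. Scale.** The unadjusted SE at 49 per arm is 3.0 × √(2/49) = 0.61. With an assumed baseline correlation of 0.6, the ANCOVA SE is 0.61 × √(1 − 0.36), about 0.49. So 0.07 is about one ninth or one seventh of an SE. On the plan's inputs, power at 49 per arm falls from 90.4% (2.00 mmHg) to 88.3% (1.93 mmHg); at 52 per arm it falls from 92.0% to 90.1%. With no effect in any arm the bias is 0.00, and false wins run at 1.9% to 2.9% per comparison against a nominal 2.5%.

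**The case against.** The strongest reply is that this hardly matters. In the sizing case the shift is at most 0.07 of 2.0 mmHg with placebo first or last, in the conservative direction, and type I error is intact when no arm has an effect. The 88.3% comes from an unadjusted t-test at 49 per arm. The baseline-adjusted primary analysis has more power: under the assumed correlations and the steeper dropout slope, a flat −2 has about 97% power as coded and 98% with the fix. All of this stands.

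It is also fair that 2.0 mmHg is a minimum for sizing rather than a prediction of equal effects; that a graded response with placebo numbered first gives little or no bias; that nothing ties cornea verticillata to IOP; and that every figure for omitting Weeks 1 and 2 rests on assumptions the documents cannot confirm. Under missingness at random, that omission loses information but adds no bias. A termination visit inside the Visit 6 window still counts as Week 4.

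Finally, the SAP plans observed-data ANCOVA, LOCF, per-protocol repeats and an MMRM. The observed-data ANCOVA avoids the coding problem but not IOP-driven dropout, where its bias was 0.02 to 0.12. The MMRM avoids both and is a good cross-check. These are secondary, however. They can show a discrepancy but do not repair the primary estimate, which would still change if the arms were renumbered.

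**Conclusion.** The concern holds. As written, the primary imputation is inconsistent with the primary analysis model, and its estimates depend on an arbitrary arm numbering. In the sizing case with 5% missing at random per arm and equally spaced codes, the shift is 0.01 to 0.07 mmHg toward no effect with placebo first or last, and 0.08 to 0.11 with placebo second or third. That range comes from the arm coding alone. Larger shifts, up to 0.26 mmHg in the illustrations, need dropout driven by Week 2 IOP together with assumed correlations, slopes and numbering.

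The error is unlikely to overturn a conclusion at 5% missing. It should still be corrected: it sits in the analysis from which superiority is declared, it affects the concentrations unequally in a study meant to choose among them, and it is easily removed. The mismatch between 5 and 30 imputations is minor. SAP Section 1 says the SAP's methods govern, and it refers to protocol Amendment 2, whereas the protocol supplied is Amendment 1.

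**What to change.** In PROC MI, replace the numeric arm code with three arm indicators, or impute separately by arm, and add Week 1 and Week 2 IOP. For example: `var d01 d02 d04 base wk1 wk2 wk4;`. Run this on the diurnal means, or per clock time with averaging after imputation. Set NIMPUTE explicitly to match the text, and record the change in SAP Section 18. With indicators, the arm numbering no longer matters.

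If the data are already unmasked, keep the planned primary analysis and report the corrected one beside it as a labelled sensitivity analysis. SAP 13.3 describes some analyses in the past tense, so this may be the case.

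Cost: a few lines of SAP text and code, at most one extra table, and no new data.

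### The SAP 13.1 pooling code omits the complete-data degrees of freedom, so pooled primary intervals are about 0.6–0.7% too narrow: a minor error with a one-option fix

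*SAP*

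**What the plan says.** SAP section 13.1 fits an ANCOVA to each of five imputed data sets, with treatment (four arms) and baseline as terms. It requests the arm differences with "lsmeans trt01pn / cl pdiff" and combines them with "proc mianalyze data = outdata2 alpha = 0.05". Only an estimate and its standard error are passed to the pooling step, and no EDF= value is given. Protocol Appendix 6 has the same structure with 30 imputations and also gives no EDF= value.

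A concentration is declared superior if the pooled two-sided p-value is below 0.05 and the estimated difference is negative. SAP section 1 says that the SAP's methods supersede the protocol's. SAP section 18 lists one change from the protocol, from ≤ 0.05 to < 0.05.

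In the sort and pooling steps, the SAP text as available shows "by trt01pn trt01pn". Protocol Appendix 6 shows "by trt01pn _trt01pn" in both places.

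**The concern.** When EDF= is absent, MIANALYZE takes the complete-data degrees of freedom as infinite and uses Rubin's large-sample formula. With little missing data that formula gives a very large number, so the pooled comparison is close to a z-test. The degrees of freedom should not exceed those of the ANCOVA fitted to complete data. The error always runs the same way: intervals slightly too narrow and p-values slightly too small.

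What is at stake is the p-value behind each superiority call, judged against a hard cut-off. The sponsor thought the difference between ≤ 0.05 and < 0.05 worth declaring, so a small avoidable shift at that same boundary is worth removing.

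**Working it through.** **Inputs.** From SAP section 5: a two-sided 5% level; "a common standard deviation (SD) of 3.5 mmHg at each time point yielding a common SD of 3.0 for the diurnal mean"; correlation 0.60 between time points; a planning difference of 2.0 mmHg; 49 subjects per arm for at least 90% power; about 5% discontinuation; 52 per arm, 208 in total. From SAP section 13.1: m = 5 imputations, and a model with four arm parameters and one covariate. The fraction of missing information, λ, is not in the documents and is assumed. The range used is 1% to 16.7%. Its upper end is the earlier once-daily cornea verticillata rate in protocol section 1.1 (76/454), as if every such subject lacked a Week 4 value.

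**1. The plan's own figure.** SD of the mean of three time points = 3.5 × √((1 + 2 × 0.6)/3) = 2.997, which agrees with 3.0. With the noncentral t distribution, power is 89.8% at 48 per arm and 90.4% at 49, so 49 is reproduced. 49/0.95 = 51.6, rounded up to 52; 4 × 52 = 208.

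**2. Complete-data degrees of freedom.** ν₀ = 208 − 5 = 203.

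**3. Formulas.** With r = λ/(1 − λ), so that 1 + 1/r = 1/λ:
- Without EDF=: ν = (m − 1)(1 + 1/r)² = 4/λ².
- With EDF= (Barnard–Rubin): ν_obs = (1 − λ) ν₀(ν₀ + 1)/(ν₀ + 3), and ν* = 1/(1/ν + 1/ν_obs).

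**4. At λ = 0.05.** ν = 4/0.0025 = 1600. ν_obs = 0.95 × 203 × 204/206 = 191.0. ν* = 1/(1/1600 + 1/191.0) = 171. The critical values are 1.9614 and 1.9740, a ratio of 1.0064.

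**5. Over the assumed range (m = 5, ν₀ = 203).**

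| λ | df without EDF= | df with EDF= | Critical value without | Critical value with | Width ratio | Reported p = 0.0500 becomes |
|---|---|---|---|---|---|---|
| 1% | 40000 | 198 | 1.9600 | 1.9720 | 1.0061 | 0.0514 |
| 5% | 1600 | 171 | 1.9614 | 1.9740 | 1.0064 | 0.0515 |
| 10% | 400 | 125 | 1.9659 | 1.9792 | 1.0068 | 0.0515 |
| 16.7% | 143 | 77 | 1.9766 | 1.9911 | 1.0073 | 0.0517 |

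With λ up to 40%, m = 5 or 30, and ν₀ = 203 or 191 (196 subjects), EDF= widens intervals by 0.6–1.1%, and a reported 0.0500 becomes 0.0514–0.0524. The number of imputations hardly matters: with m = 30 and λ = 5%, the ratio is again 1.0064.

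**6. Size in mmHg.** With a pooled standard error of about 0.49 (from the simulation below), the half-width changes by (1.9740 − 1.9614) × 0.49 = 0.006 mmHg, against a planning difference of 2.0 mmHg.

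**7. Operating characteristics.** The SAP's imputation and ANCOVA steps were simulated with 52 per arm, 5–16.7% missing, an assumed baseline correlation of 0.6 and 3000 runs per scenario. The Monte Carlo standard error near 5% is √(0.05 × 0.95/3000) = 0.4 points.
- Null, 5% missing, m = 5: rejection per contrast 4.0–4.2% without EDF= and 3.8–4.1% with it.
- All null scenarios without EDF=: 2.7–4.7%.
- Decisions changed by EDF= across scenarios: 0.08–0.18% of contrasts.
- True difference of 2.0 mmHg: power 98.0–98.6% either way.

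**The case against.** The strongest reply is that this does not matter. The half-width moves by 0.006 mmHg, few decisions change, and the plan openly tests three concentrations at 0.05 each without adjustment in Phase 2. That stands as an argument about size.

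It does not show that the degrees of freedom are right. Simulated rejection falls below 5% largely because of another feature of the same code: treatment enters the imputation as one linear numeric variable, which is conservative under the null. With treatment imputed as four categories, rejection at 5% missing was 5.0% without EDF= and 4.9% with it (18,000 contrasts, Monte Carlo error about 0.2 points).

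Three stronger readings are tempting, and the documents do not support them:

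- **That the primary test exceeds its 5% level.** Comparing quantiles alone suggests 5.14–5.17%, but the planned procedure did not exceed 5% in simulation.
- **That every MCMC analysis in SAP Table 13-1 is affected.** The SAP prints its MIANALYZE code for the ANCOVA. For the two-sample t-tests it specifies t-distribution intervals and no pooling call. If the same call were used there, complete-data df would be 2 × 52 − 2 = 102. At λ = 5% the df would be 1600 instead of 90 and the intervals 1.27% too narrow, but that use is inferred.
- **That the BY list merges contrasts against different arms.** Read literally, "by trt01pn trt01pn" would pool all differences sharing a first arm as if they were imputations of one quantity. If placebo is coded 4 and each concentration is truly at −2 mmHg, the 0.01% row would average −0.69 (SE 1.12) instead of −1.99 (SE 0.49). But protocol Appendix 6 has the underscore, SAP section 13.1 says the three differences are shown separately, SAP section 18 declares no such change, and a leading underscore is easily lost when a PDF is converted to text. That `_Imputation_` kept its underscores in the same block is weak evidence the other way. The placebo coding is also an assumption.

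**Conclusion.** The omission is real, its direction is certain, and it does not depend on how the PDF was read. It is minor: it could alter a superiority call only when the correct p-value lies between 0.050 and about 0.0515. The size rests on the assumed missing-information range, 208 analysed subjects and m = 5, and it is insensitive to each. The documents do not support a claim of inflated type I error. The BY statement is a point to verify in the source file, not an established error.

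**What to change.** In SAP section 13.1, add `edf=` to the PROC MIANALYZE statement, set to the actual residual degrees of freedom of the complete-data ANCOVA: N − 5, or `edf=203` for 208 subjects. If MIANALYZE also pools the MCMC two-sample t-tests, use the two-arm residual degrees of freedom there (102 for 52 per arm).

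While the code is open, check the source SAP to confirm that the second variable in both BY statements is `_trt01pn`, and restore it if it is missing.

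The cost is one option in the code and one look at the source file. P-values become very slightly larger and intervals very slightly wider. Study conduct and sample size do not change.
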